5.3 Treatment Duration and Confirmation of Progression

Subjects will continue treatment until disease progression, intolerable toxicities, or withdrawal of consent.

In patients with initial disease progression substantiated by radiographic imaging per RECIST 1.1, study treatment may continue until repeat imaging is conducted, at least 4 weeks and no later than 8 weeks later, under the following conditions:

- No worsening of ECOG Performance Status
- No clinically relevant increases in disease-related symptoms thought to be associated with disease progression
- No requirement for intensified management of disease-related symptoms exists, including increased analgesia, radiotherapy, or other palliative care.

5.4 Concomitant Medications/Treatments

All treatments that the investigator considers necessary for a subject's welfare may be administered at the discretion of the investigator in keeping with the community standards of medical care. All concomitant medication will be recorded on the case report form (CRF) including all prescription, over-the-counter (OTC), herbal supplements, and IV medications and fluids. If changes occur during the trial period, documentation of drug dosage, frequency, route, and date will also be included on the CRF.

No other anti-cancer therapy (chemotherapy, hormonal therapy, radiation therapy, surgery, immunotherapy, biologic therapy, or tumor embolization) or investigational agent may be used from 28 days days prior to C1D1 until study treatment discontinuation.

5.5 Duration of Study Participation

The study duration per subject will be up to 28 days of screening, up to an estimated 12 months on treatment (until disease progression, intolerable toxicities, or withdrawal of consent), and 30 days of follow-up. Survival follow-up will continue until death (estimated approximately 6 months).

5.6 Removal of Patients from Protocol

Patients will be removed from the study when any of the criteria listed in Section 6.5 apply. Notify the Principal Investigator, and document the reason for study removal and the date the patient was removed on the Case Report Form. The patient should be followed-up per protocol.

5.7 Evaluable for toxicity

Any patient who receives at least one dose of investigational product (telatinib) is evaluable for toxicity and will be included in the safety analysis.

5.8 Subject Replacement

Subjects who withdraw from the study prior to starting study treatment (telatinib) will be replaced.

6.0 STUDY PROCEDURES

6.1 Screening/Baseline Procedures

Assessments performed exclusively to determine eligibility for this study will be done only after obtaining informed consent. Assessments performed for clinical indications (not exclusively to determine study eligibility) may be used for baseline values even if the studies were done before informed consent was obtained.

All screening procedures must be performed within 28 days prior to C1D1 unless otherwise stated. Baseline procedures not used for eligibility verification may occur on C1D1 of treatment. The screening/baseline procedures include:

6.1.1 Informed Consent

6.1.2 Medical history and record review

Relevant medical history, including history of current disease and information regarding underlying diseases, will be recorded at Screening.

6.1.3 Demographics

Age, sex, race, ethnicity

6.1.4 Review subject eligibility criteria

6.1.5 Physical exam including weight, height, vital signs, and ECOG Performance Status

6.1.6 Adverse event assessment

Baseline symptoms will be assessed at Screening. See section 7.0 for Adverse Event monitoring and reporting.

Duration (start and stop dates and times), severity/grade, outcome, treatment and relation to study drug will be recorded on the case report form (CRF).

6.1.7 Concomitant Medications Review

6.1.8 Laboratory Evaluations

- Hematology (Complete blood count (CBC) with differential)
- Serum chemistries (Comprehensive metabolic panel (CMP)), including: glucose, sodium, potassium, chloride, carbon dioxide, anion gap, blood urea nitrogen, creatinine, calcium, total bilirubin, total protein, albumin, alkaline phosphatase, aspartate aminotransferase, alanine aminotransferase
- Tumor markers
 - o HCC: AFP, CA19-9
 - o Gastric: CEA, CA19-9
- Thyroid panel (T3 Free, T4 Free, thyroid stimulating hormone)
- Coagulation (PT, INR, aPTT)
- Urinalysis (including urine protein)

6.1.9 Pregnancy Testing for WOCBP (urine or serum)

6.1.10 Imaging (CT chest/abdomen/pelvis and/or MRI) (within 28 days prior to *registration*)

6.1.11 ECG

6.1.12 Research stool sample collection and completion of 24-hour food recall and stool survey

May be collected up to 4 weeks prior to C1D1 or on C1D1. The 24-hour food recall and stool survey should be completed on the same day as the stool sample collection, if feasible (not required).

6.2 **Procedures During Treatment**

6.2.1 Prior to Each Treatment Cycle

- Physical exam, weight, vital signs, ECOG Performance Status
- Hematology
- Serum chemistries
- Urinalysis

6.2.2 Each Cycle Day 1

- Pembrolizumab administration
- Adverse events assessment
- Concomitant medications review
- Tumor markers
- Thyroid panel (TSH with reflex to T3 and T4 if TSH is abnormal) (even cycles only)

- Fasting research blood collection (odd cycles only beginning with C1D1) (patients must fast for 8 hours prior to blood collection, water is allowed)
- Research stool sample collection, completion of 24-hour food recall, and stool survey (C3D1 only). The 24-hour food recall and stool survey should be completed on the same day as the stool sample collection, if feasible (not required).

6.2.3 Throughout the treatment period

- Telatinib self-administration and completion of dosing diary
- Drug supply and dosing diary will be returned at the next Cycle Day 1 (or for the last cycle, at the end-of-treatment visit) for compliance diary review and pill count.
- Imaging as per standard of care or every 9 weeks for response assessment (RECIST 1.1)
 - Upon initial radiographic disease progression per RECIST 1.1, treatment may continue until confirmation of progression at least 4 weeks and no later than 8 weeks later (see Section 5.3).

6.2.4 30 days after treatment termination (+/- 7 days)

- Physical exam, vital signs, weight, ECOG Performance Status
- Hematology
- Serum chemistries
- Tumor markers
- Adverse events assessment
- Concomitant medications review
- If indicated: Imaging (CT or MRI) with response assessment (RECIST 1.1)
- Fasting research blood collection (patients must fast for 8 hours prior to blood collection)

6.3 Follow-up Procedures

Patients will be followed every 12 weeks (+/- 14 days) after completion of (or early withdrawal from) study treatment until death for survival and progression assessment via medical record review, telephone contact, or in-clinic contact.

6.4 Time and Events Table

	Screening/	Each Cycle Day 1	End of Treatment	Survival Follow-up
Procedure	Baseline (Within 4 weeks of C1D1)	(+/- 3 days) (each cycle = 3 weeks / 21 days)	30 days after drug discontinuation (+/- 7 days)	Every 12 Weeks (+/- 14 days) until death
Informed Consent	Х			
Medical History and record review	х			
Demographics	х			
Review subject eligibility criteria	х			
Physical Exam	х	х	х	
Height (at screening only) and weight	х	Х	Х	
Vital signs	Х	Х	Х	
ECOG Performance Status	x	х	Х	
Adverse Event Assessment	х	х	Х	
Concomitant Medications	х	х	Х	
Hematology	Х	Х	Х	
Chemistry	Х	Х	Х	
Tumor markers	Х	Х	Х	
Thyroid panel (TSH with reflex to T3 and T4 if TSH is abnormal)	x	X (even cycles only)		
Coagulation (PT, INR, aPTT)	Х			
Urine or serum pregnancy test	х			
Urinalysis	X	X		
ECG	Х			
CT Scan (Chest, Abdomen, Pelvis) and/or MRI	X1	As per standard of care (or every 9 weeks for response assessment by RECIST 1.1) ²		
Pembrolizumab Administration		х		
Telatinib Administration and Dosing Diary completion		X (continuous throughout treatment period) ³		
Telatinib Dosing Diary Review and pill counts ³		Х	Х	

Protocol Version 4 dated 15MAR2023

IIT2020-11-[name]-TELAT

	Screening/	Each Cycle Day 1	End of Treatment	Survival Follow-up
Procedure	Baseline (Within 4 weeks of C1D1)	(+/- 3 days) (each cycle = 3 weeks / 21 days)	30 days after drug discontinuation (+/- 7 days)	Every 12 Weeks (+/- 14 days) until death
Research blood collection		X4	Х	
Research stool sample collection, completion of 24- hour food recall and stool survey ⁵	X5	X5		
Survival and progression assessment (by medical record review, phone call, or clinic visit)				х

¹ Screening/baseline imaging to be conducted within 28 days prior to *registration*.

² Upon initial radiographic disease progression, treatment may continue until repeat imaging is conducted 4-8 weeks later (see Section 5.3).

³ Subjects will be given a telatinib dosing diary at Cycle 1 Day 1, and at Day 1 of each subsequent cycle while taking telatinib. The completed diary and remaining drug supply will be collected at the next cycle Day 1 (or for the last cycle, at the end-of-treatment visit) for a pill count and diary review.

⁴ Fasting research blood collection will occur every odd cycle beginning with C1D1 and at the end-oftreatment visit. (patients must fast for 8 hours prior to blood collection, water is allowed)

⁵ Research stool sample collection and completion of 24-hour food recall and stool survey will occur at screening/baseline (within 4 weeks of C1D1 or on C1D1) and C3D1 (to be collected +/- 3 days of cycle start).

6.5 Removal of Subjects from Study

Patients can be taken off the study treatment and/or study at any time at their own request, or they may be withdrawn at the discretion of the investigator for safety, behavioral or administrative reasons. The reason(s) for discontinuation will be documented and may include:

- 6.5.1 Patient voluntarily withdraws (follow-up permitted);
- 6.5.2 Patient withdraws consent (termination of treatment and follow-up);
- 6.5.3 Patient is unable to comply with protocol requirements;
- 6.5.4 Patient demonstrates disease progression (unless continued treatment with study drug is deemed appropriate at the discretion of the investigator);
- 6.5.5 Patient experiences toxicity that makes continuation in the protocol unsafe;
- 6.5.6 Treating physician determines continuation on the study would not be in the patient's best interest;
- 6.5.7 Patient becomes pregnant (pregnancy to be reported along same timelines as a serious adverse event);
- 6.5.8 Development of second malignancy (except for basal cell carcinoma or squamous cell carcinoma of the skin) that requires treatment, which would interfere with this study;
- 6.5.9 Lost to follow-up. If a research subject cannot be located to document survival after a period of 1 year, the subject may be considered "lost to follow-up." All attempts to contact the subject during the one year must be documented. This will be reviewed during an interim data monitoring visit.

7.0 ADVERSE EVENTS (AE)

7.1 Definitions

7.1.1 Adverse Event

An adverse event is any untoward medical occurrence associated with use of a drug in humans, whether or not considered drug related.

7.1.1.1 Laboratory test abnormalities

A laboratory test abnormality considered clinically relevant (e.g., causing the subject to withdraw from the study, requiring treatment or causing apparent clinical manifestations, result in a delay or dose modification of study treatment, or judged relevant by the investigator), is considered an adverse event.

7.1.2 Serious Adverse Events (SAE)

An adverse event is considered "serious" if, in the view of either the investigator or sponsor, it results in any of the following outcomes:

- Death.
- A life-threatening adverse event.
- In-patient hospitalization or prolongation of existing hospitalization.
- A persistent or significant incapacity or substantial disruption of the ability to conduct normal life functions
- A congenital anomaly/birth defect.
- Important medical events that may not result in death, be life-threatening, or require hospitalization may be considered serious when, based upon appropriate medical judgment, they may jeopardize the patient or subject and may require medical or surgical intervention to prevent one of the outcomes listed in this definition. Examples of such medical events include allergic bronchospasm requiring intensive treatment in an emergency room or at home, blood dyscrasias or convulsions that do not result in inpatient hospitalization, or the development of drug dependency or drug abuse.

7.1.3 Unanticipated Problem Involving Risk to Subjects or Others (UPIRSO)

UPIRSOs include any incident, experience, or outcome that meets all of the following criteria:

- Unexpected (in terms of nature, severity, frequency) given (a) the research procedures that are described in the protocol-related documents, such as the IRB-approved research protocol and informed consent document; and (b) the characteristics of the subject population being studied;
- Related or possibly related to participation in the research (possibly related means there is a reasonable possibility that the incident, experience, or outcome may have been caused by the procedures involved in the research); and
 - Suggests that the research places subjects or others at a greater risk of harm (including physical, psychological, economic, or social harm) than was previously known to an individual or group of individuals (including research subjects, research staff, or others not directly involved in the research).

7.1.4 Suspected Unexpected Serious Adverse Reaction (SUSAR)

Suspected unexpected serious adverse reactions (SUSARs) include adverse events that are deemed unexpected, serious, and as having a reasonable possibility of a causal relationship with the study drug.

7.2 Principal Investigator Responsibilities for Safety Monitoring

The investigator or designee is responsible for ensuring that adverse events (both serious and non-serious) observed by the clinical team or reported by the subject which occur from treatment administration on Cycle 1 Day 1 and until 30 days following the last dose of the study drug or until initiation of a new anticancer therapy (whichever occurs first), are fully recorded in the subject's medical records. Source documentation must be available to support all adverse events.

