7.2.1 AE Documentation

A laboratory test abnormality considered clinically relevant (e.g., causing the subject to withdraw from the study, requiring treatment or causing apparent clinical

manifestations, result in a delay or dose modification of study treatment, or judged relevant by the investigator), should be reported as an adverse event.

The investigator or sub-investigator (treating physician if applicable) will document the following for all adverse events (both serious and non-serious):

- Event term- according to the NCI Common Terminology Criteria for Adverse Events (CTCAE) version 5. The CTCAE current version is available at http://ctep.cancer.gov/reporting/ctc.html
- Description of the event
- Date of onset and resolution
- Expectedness of the toxicity
 - Expected events are those that have been previously identified as resulting from administration of the agent. An adverse event is considered unexpected, for expedited reporting purposes only, when either the type of event or the severity of the event is not listed in:
 - the current known adverse events listed in this protocol;
 - the drug package insert; and/or
 - the current Investigator's Brochure
- Grade of toxicity
 - Attribution of relatedness to the investigational agent- (this must be assigned by an Investigator, sub-investigator, or treating physician)
 - Attribution categories are as follows:
 - Definite: The AE is clearly related to the study treatment.
 - Probable: The AE is likely related to the study treatment.
 - Possible: The AE may be related to the study treatment.
 - Unlikely: The AE is doubtfully related to the study treatment.
 - Unrelated: The AE is clearly NOT related to the study treatment.
- Action taken as a result of the event, including but not limited to; no changes, dose interrupted, reduced, discontinued, etc. or action taken with regard to the event, i.e. no action, received conmed or other intervention, etc.
- Outcome of event

Source documentation must be available to support all AEs.

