7.2.2 Duration of AE monitoring

All patients experiencing an adverse event, regardless of its relationship to study drug, will be monitored until:

- the AE resolves or the symptoms or signs that constitute the AE return to baseline
- any abnormal laboratory value deemed an AE as per section 7.1.1.1, has returned to baseline
- there is a satisfactory explanation other than the study drug for the changes observed
- death, or
- until 30 days following last dose of study drug or until initiation of a new anticancer therapy (whichever occurs first)

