7.3 Safety Reporting Requirements

7.3.1.1 Reporting to the Principal Investigator

The Principal Investigator must be notified by study staff or co-investigators within 24 hours of learning of any serious adverse events, regardless of attribution, occurring during the study or within 30 days of the last administration of the study drug or until initiation of a new anticancer therapy (whichever occurs first).

Contact for Expedited Reporting:

[name], MPH [contact]; [contact]

Alternate Contact for Expedited Reporting:

[name] [contact]; [contact]

7.3.1.2 Reporting to DSMC:

Serious Adverse Events deemed to be related to the protocol and on-study deaths, including death of a research subject unless the death is expected (e.g. due to disease progression) are to be reported to the DSMC within 24 hours of awareness. Hardcopies or electronic versions of the MedWatch Form 3500A (Mandatory Reporting) or a narrative report, along with any other supporting documentation available, should be submitted to the DSMC Coordinator. The DSMC Coordinator will forward the information to the DSMC Chair, and/or medical monitor. The DSMC Chair will review all documentation upon receipt from the DSMC Coordinator and determination of whether the following actions are required: 1) takes action immediately, 2) convenes a special DSMC session (physical or electronic), or 3) defers the action until a regularly scheduled DSMC meeting. Reports to be emailed to the DSMC team at [contact].

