10.5.2 Safety Monitoring

High Risk Monitoring

Oversight of the progress and safety of the study will be provided by the PI. The PI will maintain continuous safety monitoring for the duration of the study by reviewing subject/study data. Adverse events and unanticipated problems are not expected, but if they occur, they will be documented and reported according to CS-IRB policies and procedures. If the PI becomes aware of any new safety information that may place subjects at increased risk than what was previously known, the IRB will be promptly notified and if warranted, enrollment may be held until the PI determines whether a modification to the study is necessary and/or the informed consent documents are updated accordingly. It is the responsibility of the principal investigator to adhere to the Data Safety Monitoring Plan throughout the life of the study.

In addition, this protocol will utilize the SOCCI Data and Safety Monitoring Committee to provide another layer of data and safety oversight. DSMC membership and responsibilities are governed by the committee charter. Every three (3) months the DSMC findings and recommendations will be reported in writing to the Principal Investigator as a summary letter which will be forwarded by the Principal Investigator or designee to the CS-IRB. The DSMC may increase or decrease the frequency of study review, at their discretion. Refer to the DSMC Charter for details of the DSMC review.

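### Monitoring of an open telatinib-related SAE may stop 30 days after the last dose, or earlier at new therapy, so its final status can stay unknown

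*Combined protocol and SAP*

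**What the plan says.** Section 7.2 has adverse events, serious and non-serious alike, recorded from Cycle 1 Day 1 "until 30 days following the last dose of the study drug or until initiation of a new anticancer therapy (whichever occurs first").

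Section 7.2.2 covers every patient with an adverse event, whatever its relation to study drug. It lists alternative points at which monitoring ends. Resolution and death are among them; the last is "until 30 days following last dose of study drug or until initiation of a new anticancer therapy (whichever occurs first").

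Section 7.2.1 states that the investigator "will document the following for all adverse events (both serious and non-serious"), and its list includes "Date of onset and resolution" and "Outcome of event".

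Section 7.3.1.1 requires the PI to be told of any SAE, whether or not it is thought related, and gives the period covered as "occurring during the study or within 30 days of the last administration of the study drug or until initiation of a new anticancer therapy".

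The schedule in 6.4 places the last adverse event assessment at the end-of-treatment visit, 30 days (+/- 7) after discontinuation. The later contacts in 6.3 and 6.4, every 12 weeks (+/- 14 days), cover survival and progression, and review of the medical record is enough. Inclusion criterion 4.1.8 requires contraception until 4 months after the last dose. Section 6.5.7 puts pregnancy on the SAE reporting timeline.

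**The concern.** A short window for general adverse events is a normal choice. What is missing is an exception for a related SAE that has not settled when the window closes. As written, the duty to monitor it lapses then, and no later contact asks how it ended.

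This matters because safety is a secondary objective and 9.3.2 promises that SAEs will be described in detail. The stopping rules count only first-cycle events (5.2.1, 9.4), so toxicity arising later is known only through ordinary adverse event recording. Section 5.2 lists haemorrhage, gastrointestinal perforation, and liver, renal and cardiac effects for telatinib, and section 1.3.3 offers only preclinical data for this drug pair. With 21 and 24 patients, each SAE outcome carries weight in the safety description.

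**Working it through.** No statistical figure bears on this point. The check sets the sections side by side and then counts days.

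**The rule applied to one case.** Suppose an SAE judged probably related to telatinib is unresolved when the patient stops treatment.

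1. Under 7.2.2 the ending points are alternatives, so the last one is enough to end monitoring even though the event has not resolved.
2. Attribution and seriousness do not change this, because the section applies to all adverse events alike.
3. The limit can come before day 30. Treatment normally ends at progression (5.3), other anticancer therapy is barred only until study treatment stops (5.4), and section 1.1 names several other agents for both diseases. The monitoring period after the last dose therefore has no guaranteed minimum length.
4. The end-of-treatment visit includes an adverse event assessment, so the event's status at about day 30 may be seen there. No adverse event assessment is scheduled afterwards.
5. The 12-weekly contacts ask about survival and progression only. The event's final status is collected only if someone looks for it unprompted.

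**Late-onset events.** Section 7.2 closes recording at the same limit. Section 7.3.1.2 still sends "Serious Adverse Events deemed to be related to the protocol and on-study deaths" to the DSMC within 24 hours of awareness, and the IRB and FDA routes (7.3.1.3, 7.3.1.4) state no end date. All of these start once somebody knows of the event; none schedules an enquiry.

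**Day counts for the secondary, pregnancy limb.** Assume that day 0 is both the last dose and the end of treatment, and that the 12-week contacts count from it.

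- Contraception period: 4 x 365.25/12 = 121.75 days.
- Part after the 30-day limit: 121.75 - 30 = 91.75 days; 91.75/121.75 = 75.4%.
- Last adverse event visit: 30 +/- 7 = day 23 to 37. From it to month 4: 121.75 - 37 = 84.75 to 121.75 - 23 = 98.75 days with no planned question.
- First contact: 84 +/- 14 = day 70 to 98. Second contact: 168 +/- 14 = day 154 to 182.
- Days of the contraception period left for the second contact to cover: 121.75 - 98 = 23.75 to 121.75 - 70 = 51.75.
- Section 5.5 estimates about 6 months of survival follow-up until death: 6 x 365.25/12 = 182.6 days.

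The second contact thus falls close to the estimated end of survival follow-up, and some patients will not be alive to answer a question then. The 75% describes the contraception period. It does not measure SAE risk.

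**The case against.** The best defence is that the limit was chosen on purpose. The version 3 entry in section 12.7 records its addition to adverse event monitoring. Section 1.2.2 describes telatinib's side effects as foreseeable and reversible, and the animal half-lives in 1.2.3 are short (about 1 hour in dogs, 2.1 to 3.4 hours in rats). Section 7.2.2 sets a minimum and does not forbid longer follow-up. Patients must be able to attend follow-up at the treating institute (4.1.10), a chart review for survival and progression may also show a hospital admission, and 10.5.2 says "The PI will maintain continuous safety monitoring for the duration of the study by reviewing subject/study data".

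Much of this stands, and it rules out several stronger readings that a reader might infer:

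- *The 30-day window is itself a mistake.* It is a deliberate choice, and the documents offer grounds for a short general window. Only the missing exception is at issue.
- *SAE notification to the PI stops at day 30.* The text of 7.3.1.1 also reaches events during the study, and the study schema counts up to 6 months of follow-up in the study duration. Section 5.5 treats the 30-day follow-up and survival follow-up separately, which favours the narrower reading. The wording is ambiguous.
- *Section 7.2.1 contradicts 7.2.2.* The resolution date and outcome are data fields. An unresolved event can be entered as such without a resolution date, as can one that ends in death.
- *Late related SAEs surface only by chance, or go unreported.* Chart review may reveal them, and the DSMC, IRB and FDA routes have no end date.
- *Three quarters of late risk is missed.* The day counts concern a contraception precaution, and the documents give no onset times for late events.

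The defence does not supply a duty to follow an open related SAE to its end. Oversight through review of collected data cannot show what was never asked for. The consent form and the DSMC charter were not available and might contain instructions on late events; the gap is shown for the protocol only.

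**Conclusion.** The point holds as a modest gap in safety follow-up. The protocol permits monitoring of an unresolved telatinib-related SAE to end 30 days after the last dose, or earlier at new therapy, and schedules no later enquiry about it. Its final status may then be missing from the detailed account that 9.3.2 promises. Related SAEs that begin later remain reportable if staff learn of them, but are not solicited.

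No number of missed events is claimed. The pregnancy and 4-month element is secondary: about 92 of 122 days of required contraception fall after the limit, under the day-0 assumption above. The primary PFS analysis does not depend on this, and the stopping rules use first-cycle events only. It is worth correcting because the correction is cheap.

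**What to change.** Keep the 30-day window for adverse events in general and leave 7.2.3 unchanged.

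- **7.2.2:** follow any open SAE at least possibly related to telatinib or the combination until resolution, stabilisation, death, loss to follow-up or withdrawal of consent, regardless of new anticancer therapy.
- **7.2 and 7.3.1.1:** record later-onset related SAEs and pregnancies, and notify the PI, whenever the team becomes aware of them. This also settles the ambiguity in 7.3.1.1.
- **Optional, 6.3 and 6.4:** add a short related-SAE and pregnancy question to the existing 12-week contacts, covering the 4 months in 4.1.8 for patients still alive. Four months is a practical limit borrowed from the contraception rule; it does not state how long adverse event risk lasts. List events after new therapy separately.

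Cost: one amendment with IRB approval (10.7.4), possible case report form and consent changes, and, if the optional part is taken up, some telephone calls in place of chart review. No new visit is needed. A few events will have attribution confounded by later therapy, which the separate listing makes visible.
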